3.2.3 Secondary Safety Endpoints

The safety endpoints will include the following:

1. All NCI-CTCAE Grade 3-5 AEs, which are defined as possibly, probably, or definitely related to rituximab.
2. All NCI-CTCAE Grade 3-5 adverse events.
3. All infection related events.
4. Treatment-related mortality, defined as death occurring at any time after randomization and possibly, probably, or definitely resulting from treatment given in the study. Study investigators will make an initial determination of the cause of death of any subject and if uncertainty remains, a final decision will be made by an independent blinded panel after reviewing all clinical and, if available, autopsy data.
5. All-cause mortality, defined as any death occurring at any time after randomization.
6. CD19+ B cell levels post treatment (note that analyses will be performed regularly per Table 6.1 through 48 weeks and quarterly thereafter as documented in Protocol Section 3.1, *Description of Study Design*).
7. Peripheral blood cell counts, liver function, and creatinine levels after treatment.

3.2.4 Exploratory Endpoints

Exploratory analysis of standardization of the PVR calculation will be based on PVR calculated from a standardized Fick calculation of cardiac output, which is a function of hemoglobin, arterial and mixed-venous saturations, and oxygen consumption according to the La-Farge and Miettinen formula. The cardiac output calculation is a function of assumed oxygen consumption according to the La-Farge calculation of values normalized for age, gender, heart rate. Calculation of a standardized Fick cardiac output will also allow for determination of the pulmonary artery capacitance (PACf). See Appendix E, *Exploratory Analysis: Standardized Fick-based Pulmonary Vascular Resistance and Pulmonary Artery Capacitance* for details.

Additionally, an exploratory analysis of the relationship between change in PVR and change in 6MWD will be addressed. Relationships with other clinical endpoints, like change in NT-proBNP, will also be explored.

3.3 Subject Disposition

3.3.1 Definition of Subject Completion

A subject is considered to have completed the study if he/she has completed Visit 16 (Week 48).

3.3.2 Discontinuation of Protocol-Specified Treatment Requirements

Protocol-specified requirements for the treatment of subjects, including regimens for investigational, concomitant, or rescue medications, as well as restrictions for disallowed medications, **will** be discontinued for any individual subject under the following conditions:

1. Any protocol-specified treatment requirement will be discontinued immediately at any time during the study at the request of the subject.
2. Investigator or DAIT/NIAID will discontinue any protocol-specified treatment requirement if the subject's health, safety, and/or well-being are threatened.
3. Protocol-specified treatment requirements for rituximab will be discontinued and replaced with appropriate therapy for any subject who experiences any of the following:
 - Significant cardiopulmonary disease **PROGRESSION** as manifested by new or worsening **Grade 3 or higher** AEs including:
 - Incompletely controlled or life threatening arrhythmias
 - Vasovagal episode occurring either during or within 12 hours following an infusion
 - Sinus bradycardia unresponsive to atropine treatment as detailed in Section 5.4.3.2, *Cardiovascular*
 - Chest pain consistent with angina or evidence of myocardial infarction
 - Cardiopulmonary arrest
 - Sustained systemic hypertension requiring additional therapy above baseline medications
 - Sustained hypotension
 - Congestive heart failure worsening from baseline level
 - Pericardial effusion or pericarditis
 - Pneumonitis progressing above baseline level
 - Bronchospasm
 - Dyspnea progressing above baseline level
 - Stridor or other indicators of respiratory compromise
 - New symptomatic pericarditis Grade 2 or higher
 - Toxicities of rituximab, if required as per Sections 5.3.5, *Criteria for Discontinuing Rituximab Infusion* and 5.4.3, *Management of Infusion Reactions/Known Toxicities to Rituximab*
4. Disease progression requiring change in Concurrent Medication as per Section 5.7, *Concurrent Medications and Therapy*.

3.3.2.1 Follow-up Requirements for All Treated Subjects

Independent of whether treated subjects have completed the full course of rituximab, the following procedures will apply:

1. If prohibited medications as defined in Section 5.6, *Prohibited Medications and Treatments* are not needed for treatment of progressive PAH, the subject will complete all scheduled study visits including all exams, procedures, assessments, and tests according to the protocol.
2. If prohibited medications as defined in Section 5.6, *Prohibited Medications and Treatments* (i.e. addition of new or a change in the dose of background PAH therapies [prostanoid, endothelin receptor antagonist, PDE-5 inhibitor, and/or guanylate cyclase stimulators] or surgical therapy) are needed for treatment of progressive PAH prior to the Week 24 visit, or if the subject withdraws consent, he/she will be asked to complete an Early Endpoint Visit as detailed in Section 6.5.5, *Early Endpoint Visit*.
3. In addition, if the subject has not withdrawn consent and has not achieved B cell recovery, follow-up clinical care must include visits at least quarterly to monitor recovery of B cells. Quarterly monitoring visits will continue until B cell recovery or for 2 years after initial treatment (whichever occurs first). Recovery is defined as the time point at which B cells recover to within 10% of baseline levels; if a baseline value is not available then recovery is defined as a B cell level of at least 90% of the lower limit of normal. During this monitoring period, AEs and SAEs will be assessed, providing the subject has not withdrawn consent, to capture any infectious event \geq Grade 3 using the NCI-CTCAE. No additional study-related data will be collected.

Subjects who have discontinued their concurrent medications prior to Week 24 for toxicity only, and not disease progression, will continue to participate in the study. They will be permitted to change medication for PAH in order to maintain control of their disease and will complete all exams, procedures, assessments, and tests according to the protocol.

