Sample Size: The study will include 30 subjects treated with rituximab and 30 subjects treated with placebo.

Data Analyses: The primary efficacy analysis of change in 6MWD from baseline to 24 weeks will be performed on the intention-to-treat (ITT) population, and will be tested using a repeated measures random effects model to model change from baseline in 6MWD as the primary outcome and treatment as the primary predictor, controlling for visit day, limitations by musculoskeletal disease, baseline levels of 6MWD, and a treatment by visit day interaction. A random slope and intercept will be fit for each subject. An unstructured covariance matrix will be assumed for the random effects. Additional covariates will be considered for this model as part of secondary analysis.

[figure not shown]
Secondary analyses will include repeating the primary analysis in the per protocol population, subgroup analyses of the primary outcome, safety analyses, exploratory analyses of the secondary endpoints, and exploratory analyses of the mechanistic endpoints.

Lay Summary:

Sixty eligible adults between the ages of 18 and 75 who have been diagnosed with SSc-PAH within the past 5 years and meet all entry criteria will be enrolled in this study. Participants will receive 2 infusions (1000 mg) of either rituximab or placebo 14 days apart.

This study will compare patients treated with rituximab to those on placebo for change in six minute walk distance (6MWD). The secondary objectives of this study are to compare treatment groups for other measures of clinical disease progression and to determine whether the effects on clinical disease progression are paralleled by changes in selected biomarkers. Additionally, the safety and tolerability of rituximab for the treatment of SSc-PAH in patients receiving stable background medical treatment with prostanoid, endothelin receptor antagonist, PDE-5 inhibitor, and/or guanylate cyclase stimulators therapy will be assessed.

FLOW DIAGRAM OF PROTOCOL

ABBREVIATIONS

6MWD	6-Minute Walk Distance
6MWT	6-Minute Walk Test
ACE	Autoimmunity Centers of Excellence
ADCC	Antibody-dependent Cellular Cytotoxicity
ADCT	Autoimmune Diseases Clinical Trials
AE	Adverse event
AECA	Anti-Endothelial Cell Antibody
ALP	Alkaline Phosphatase
ALT	Alanine Aminotransferase
ANAs	Serum Antinuclear Antibodies
ANCOVA	Analysis of Covariance
Anti-B23	Antibody to the B23 antigen
Anti-CENP-B	Antibody to the CENP-B (centromere) antigen

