5.7 Concurrent Medications and Therapy

5.7.1 Background PAH Therapy

From the time of study entry, subjects are to remain on background PAH medical therapy with either a single agent or a combination of prostanoid, endothelin receptor antagonist, PDE-5 inhibitor, and/or guanylate cyclase stimulators as per the entry criteria. Doses must remain stable through the week 24 primary endpoint visit.

Investigational prostanoids, endothelin receptor antagonists and PDE-5 inhibitors are permitted if the drugs are already in use for the treatment of PAH but are not currently licensed for this use by the FDA.

Permitted Dose modifications:

- Toxicity management for any of the four classes of drugs
- Increase in prostacyclin dose of up to 10% for worsening disease independent of route of administration.

Other PAH medications, such as diuretics and anti-coagulation, should be managed by the treating physician according to institutional practice. Changes in diuretics and anti-coagulants are permitted throughout the duration of the study.

Stabilization/clinical improvement in PAH should result in no change to background therapy for the duration of the subject's participation in the study.

If a change in medical (beyond the 10% increase in prostacyclin dose) or surgical therapy is necessary for the treatment of progressive PAH before the week 24 primary endpoint visit then the subject will complete an Early Endpoint visit (see Section 6.5.6) and procedures in Section 3.3.2.1, *Follow-up Requirements for All Treated Subjects* numbers 2 and 3 will be followed.

After the week 24 endpoint visit, the doses of background therapies for PAH may be increased and other agents may be added as needed to treat worsening PAH if the subject experiences any one of the following:

- a deterioration in functional class and a decrease in 6MWD by $> 20\%$,
or
- the development of signs and symptoms of clinical right heart failure, such as worsening edema, ascites, and/or weight gain,
or
- other objective data suggesting clinical deterioration, such as worsening cardiopulmonary hemodynamics as evidenced by a $\geq 20\%$ decrease in cardiac output, a $\geq 20\%$ increase in mPAP, or a $\geq 20\%$ increase in PVR.

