7.3.2 Collection Period

Adverse events NCI-CTCAE grade 2 and above will be collected from the time the subject signs the informed consent until he/she initiates study intervention or until he/she is determined to be ineligible to receive study intervention, if the investigator determines that the adverse event is related to a study-mandated procedure, treatment, or change in treatment.

For all participants, adverse events NCI-CTCAE grade 2 and above will be collected from the time of initiation of study intervention (i.e., the administration of the first dose of study drug/study drug as defined in Section 6.5.3.1, *Visit 3 [Day 0]*) until he/she completes study participation or until 30 days after he/she prematurely withdraws (without withdrawing consent) or is withdrawn from the study.

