The 6MWD has been the most utilized endpoint in PAH trials, and a 33m improvement from baseline is considered clinically significant [160]. For sample size calculations, we assume a change from baseline of 0m for the placebo arm and 33m for the rituximab arm. An effect size of this magnitude is attainable in a 24 week period, and has been seen in as little as 12 weeks in studies using vasodilators. Assuming a standard deviation of 58m (a best guess based on prior studies) and a 20% drop out rate, ASC01 would be powered at 50% to detect a treatment group difference of 33m for this phase II study. If a significant result is found for this primary efficacy endpoint and no safety signals emerge, this study could provide a definitive conclusion about this treatment. In order to achieve 80% power, the true difference between treatment groups would have to be at least 50m. While other studies evaluating other drugs have seen this magnitude of difference in similar timeframes, we have no data on rituximab to suggest the true difference is at least 50m. Furthermore, rituximab would be interesting as a therapy option if the effect size is as small as 33m.

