7.2.2. Primary Analysis of the Primary Endpoint

The primary efficacy analysis for this study is designed to test the scientific hypothesis that rituximab has a beneficial clinical impact on SSc-PAH as measured by improvement or stabilization in 6MWD between baseline to 24 weeks in patients treated with standard of care plus rituximab than in patients treated with standard of care plus placebo. Operationally for this study, this scientific hypothesis will be examined by formally testing the following statistical hypothesis:

H_0 : The mean change in 6MWD between baseline and 24 weeks does not differ between individuals treated with rituximab and those treated with placebo
($\bar{\delta}_{\text{rituximab}} = \bar{\delta}_{\text{placebo}}$ where $\bar{\delta}_x = \text{mean 6MWD at 24 weeks} - \text{mean 6MWD at baseline}$)

versus

H_A : The mean change in 6MWD between baseline and 24 weeks is more beneficial in those individuals treated with rituximab than in those treated with placebo
($\bar{\delta}_{\text{rituximab}} < \bar{\delta}_{\text{placebo}}$ where $\bar{\delta}_x = \text{mean 6MWD at 24 weeks} - \text{mean 6MWD at baseline}$)

While this hypothesis is inherently one-sided, a two-sided test at $\alpha=0.05$ will be used to evaluate the treatment effect at 24 weeks. This primary hypothesis will be tested using a repeated measures random effect model to model the distance walked as a function of treatment, visit week and a treatment by visit week interaction. Additionally, a quadratic term for visit week will be included in the model. A random slope and intercept will be fit for each subject using a separate unstructured covariance matrix for each treatment group. The model will include only 6MWD data up to Week 24. All available data up to Week 24 will be used for subjects who terminate early from the study. All unscheduled visits that occur prior to Week 24 will also be included in the analysis.

Model estimates and standard errors of the distance walked and change from baseline in distance walked will be presented at baseline and Week 24, along with the differences between arms. An appropriate contrast will be used to test the difference (baseline to Week 24) between treatment arms.

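### Subjects who need new or changed PAH therapy for progression before Week 24 have a full pre-rescue Early Endpoint Visit, but no scheduled efficacy assessment and only limited safety follow-up after it

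*Protocol*

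**What the plan says.** Protocol 3.3.2.1 sets follow-up for all treated subjects in three items.

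- **Item 1:** if prohibited medications "are not needed for treatment of progressive PAH, the subject will complete all scheduled study visits including all exams, procedures, assessments, and tests".
- **Item 2:** a subject who needs such therapy for progressive PAH before Week 24 is asked to complete an Early Endpoint Visit.
- **Item 3:** a subject whose B cells have not recovered has at least quarterly B-cell monitoring, for up to two years after initial treatment. On safety it says "During this monitoring period, AEs and SAEs will be assessed, providing the subject has not withdrawn consent, to capture any infectious event" of Grade 3 or higher, and it rules out collecting any other study data.

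Protocol 5.7.1 repeats the route for progression: "then the subject will complete an Early Endpoint visit (see Section 6.5.6) and procedures in Section 3.3.2.1", naming items 2 and 3 only. Protocol 6.5.6 fills the Early Endpoint Visit before Week 24 with all Week 24 procedures, including the catheterization, to be done before therapy changes. Protocol 8.5.5 and SAP 7.2.2 bring the resulting walk into the primary model.

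Grade 2+ adverse events are collected to the end of participation or "until 30 days after he/she prematurely withdraws (without withdrawing consent) or is withdrawn from the study" (Protocol 7.3.2). Vital status is sought at Week 104 (6.5.4.13).

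Two other groups of therapy changers are treated differently. Under 3.3.2.1, subjects who change PAH drugs before Week 24 because of toxicity complete everything. Under 5.7.1, drugs may be added for worsening after Week 24 and no exit is prescribed.

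**The concern.** Study drug is two infusions, nominally at Day 0 and Week 2, so the end of treatment does not explain ending assessments. What ends them is early progression, which is closely tied to the outcome and may differ in frequency between arms.

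Two things are at stake.

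- **Efficacy.** For these subjects no visit measures 6MWD, SF-36, SHAQ or DLCO at the real Week 24 or Week 48. Their values at those times come from the mixed models, carried forward from pre-rescue data.
- **Safety.** The safety endpoints in Protocol 3.2.3 include all Grade 3-5 events, all infection-related events and treatment-related mortality, yet most of the planned 48 weeks would lack full collection. What remains after 30 days depends on B-cell recovery. That probably differs by arm, because placebo subjects are not depleted by study drug (an inference; the documents do not state it). Ascertainment after exit may therefore differ by arm too.

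**Working it through.** **1. Does the exit follow from the text?** No single sentence says that visits stop, so the passages must be read together.

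- 3.3.2.1 item 1 attaches the full schedule to subjects who do not need the therapy. 5.7.1 sends those who do to items 2 and 3.
- 6.5.5 places subjects who reach endpoint early in quarterly monitoring alongside Week 48 completers.
- 6.5.6 describes the progression visit in terms of withdrawal.
- 3.1.1 treats the Early Endpoint Visit as the alternative to Visit 16 for communicating B-cell status.
- Against this, 3.3.3 does not list progression among the withdrawal conditions.

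The exit is the natural reading, but it is not stated outright. The 30-day limit in 7.3.2 applies only if the exit counts as a withdrawal.

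**2. The plan's own figure that involves loss of subjects.** The inputs are:

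- "The study will include 30 subjects treated with rituximab and 30 subjects treated with placebo" (Protocol synopsis);
- "we assume a change from baseline of 0m for the placebo arm and 33m for the rituximab arm" and "Assuming a standard deviation of 58m (a best guess based on prior studies) and a 20% drop out rate" (Protocol 8.1);
- a two-sided test at 0.05 (SAP 7.2.2).

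Evaluable per arm: 30 × (1 − 0.20) = 24.
Standard error: 58 × √(2/24) = 16.74 m.
Standardised difference: 33 / 16.74 = 1.971.
Power: Φ(1.971 − 1.960) = 50.4% (48.8% with the noncentral t).

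The stated 50% is reproduced. The documents do not say whether the 20% includes early-endpoint subjects, so this figure does not show how many there would be.

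**3. Full adverse event collection lost per subject.** With exit at week t and 30 days = 30/7 = 4.29 weeks, collection ends at t + 4.29 and the loss is 48 − t − 4.29.

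| Exit week | Grade 2+ collection ends (week) | Weeks lost of 48 | Share of 48 weeks |
|---|---|---|---|
| 2 | 6.3 | 41.7 | 87% |
| 4 | 8.3 | 39.7 | 83% |
| 12 | 16.3 | 31.7 | 66% |
| 20 | 24.3 | 23.7 | 49% |
| 24 (limit) | 28.3 | 19.7 | 41% |

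These are weeks without full Grade 2+ collection. Some of them still carry Grade 3+ infection capture while B cells have not recovered. SAP 8.2 lists those infections separately and leaves them out of the tabulations unless otherwise specified.

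**4. Distance extrapolated.** The last scheduled walk is the one at week t, so the gap is 24 − t to Week 24 and 48 − t to Week 48. An exit at Week 4 leaves gaps of 20 and 44 weeks; an exit at Week 20 leaves 4 and 28.

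**5. Can the planned analyses stand in?** SAP 7.2.3 item 3 and the Week 48 model in SAP 7.3.2 use a covariate for PAH-therapy change. Subjects who changed for early progression supply no later values to inform it. The joint longitudinal/survival model in SAP 7.2.3 item 4 is optional. It can vary the missing-data assumptions but cannot compare them with observed post-rescue data.

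**6. Deaths.** Under SAP 8.3.2 relatedness is available only for deaths reported as SAEs. Protocol 7.3.5 records new SAEs for 30 days after premature withdrawal, and later only as item 3 of 3.3.2.1 provides. A death after that window and outside the infection rule counts towards all-cause mortality with no relatedness assessment.

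**The case against.** The strongest defence is that the pre-rescue endpoint is deliberate. Protocol 1.5.1 requires stable background therapy so that changes in PAH drugs do not confound the comparison, and the Early Endpoint Visit secures a complete assessment before the change. That stands, and the fix should preserve it.

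Several stronger readings are tempting, and the documents do not support them.

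- **That progressors have no Week 24-type efficacy data.** They have the whole battery, earlier and pre-rescue, and the walk is used. What is missing is everything afterwards.
- **That every endpoint suffers.** Adding a PAH agent is itself a clinical-worsening event (SAP 7.3.3), the therapy-change endpoint uses the first change (SAP 7.3.4), and vital status is sought at Week 104. These endpoints are largely unaffected.
- **That early progressors are the only subjects removed.** Pregnancy (5.8.2), persistent hypotension at a second infusion attempt (5.3) and the general conditions in 3.3.3 also end participation. The selectivity is among therapy changers.
- **That B-cell-depleted subjects go unobserved.** They keep at least quarterly visits with Grade 3+ infection capture.
- **That no planned analysis addresses the problem.** The joint model does, through assumptions only.
- **That all drug is in by Week 2.** A withheld second infusion may be given up to four weeks after the first (5.3.6).
- **That 20% of 60, or 12 subjects, bounds the trial-level loss.** The documents give no rescue rate and do not tie the 20% to rescue, so no total follows.

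**Conclusion.** The gap is real and limited to the period after rescue. Subjects whose PAH therapy must change for progression before Week 24 contribute a full pre-rescue assessment and then no scheduled efficacy data. Among therapy changers the loss falls on early progressors, so missingness is related to outcome, and the data needed to check the model's extrapolation are never collected.

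Per subject, an exit between Week 2 and Week 24 costs about 42 to 20 of 48 weeks of full adverse event collection. This assumes that the exit counts as premature withdrawal under 7.3.2. The number of such subjects, and any imbalance between arms, cannot be derived from the documents.

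The plan does not become unworkable. The primary model remains estimable, and time to clinical worsening, first PAH-therapy change and all-cause mortality are largely intact. The text should be amended because the missing follow-up can be obtained through visits that already exist, and because the passages in 3.3.2.1, 3.3.3, 5.7.1, 6.5.5, 6.5.6 and 7.3.2 need reconciling in any case.

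**What to change.** **Protocol.** Amend 3.3.2.1 item 2, 5.7.1 and 6.5.6 so that, after the Early Endpoint Visit, a subject who has not withdrawn consent continues the existing Table 6.1 visits and full AE/SAE collection through Week 48. No second catheterization is needed if one was done at the Early Endpoint Visit. State plainly in 3.3.3 whether progression is a withdrawal. Correct the references in 3.3.2.1 and 3.3.3 that point to 6.5.5 for the Early Endpoint Visit, which is 6.5.6.

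**SAP.** Sections 7.1.2 and 7.2.2 take all walks to Week 24, so post-rescue walks would enter the primary model by default and change what it estimates. Add an explicit rule: for a subject with an Early Endpoint Visit for progression, the primary model uses walks up to and including that visit. Flag post-rescue values and add one sensitivity analysis that includes them. Also reconcile the note in 7.3.1, under which subjects lost before Week 24 contribute only screening PVR, with the Early Endpoint catheterization.

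**Cost.** This takes one protocol amendment and a short SAP change, with no new visit type. It changes no dose or rescue rule. The downside is visit burden for a few sicker subjects, some of whom may decline. No gain in primary power is claimed, because the primary model keeps the same walks. Data for subjects who have already exited cannot be recovered, and this should be stated as a limitation.
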